10 STATISTICAL ANALYSIS PLAN

This section outlines the statistical analysis strategy and procedures for the study. If, after the study has begun, changes are made to primary and/or key secondary hypotheses, or the statistical methods related to those hypotheses, then the protocol will be amended (consistent with ICH Guideline E-9). Changes to exploratory or other non-confirmatory analyses made after the protocol has been finalized, but prior to the conduct of any analysis, will be documented in a supplemental Statistical Analysis Plan (sSAP) and referenced in the Clinical Study Report (CSR) for the study. Separate analysis plans may be developed for biomarker

analysis and genetic data analysis. Post-hoc exploratory analyses will be clearly identified in the Clinical Study Report. The PRO analysis plan will also be included in the sSAP.

10.1 Statistical Analysis Plan Summary

Key elements of the Statistical Analysis Plan are summarized below; the comprehensive plan is provided in Sections 10.2 to 10.12.

Study Design Overview	A Phase III, Randomized, Open-label Study to Evaluate Pembrolizumab as Neoadjuvant therapy and Pembrolizumab plus Radiotherapy with and without Chemotherapy as Adjuvant Therapy for Stage III-IVA Resectable Locoregionally Advanced Head and Neck Squamous Cell Carcinoma (LA HNSCC)
Treatment Assignment	
In this study, 714 participants have been enrolled, which will result in approximately 462 participants whose tumors express PD-L1 CPS\geq10 (based on a prevalence rate of ~65% of the CPS\geq10 participants among all participants) and approximately 680 participants whose tumors express PD-L1 CPS\geq1 (based on a prevalence rate of ~95% of the CPS\geq1 participants among all participants) will be randomized in a 1:1 ratio between 2 treatment arms:
 
1. Pembrolizumab as neoadjuvant therapy and in combination with RT \pm cisplatin as adjuvant therapy after surgical resection (referred as pembrolizumab arm)2. No neoadjuvant therapy and RT \pm cisplatin as adjuvant therapy after surgical resection (referred as SoC arm) 
This study will be conducted as an open-label study. Stratification factors are as follows:
 
• Primary tumor site (oropharynx/oral cavity vs. larynx vs. hypopharynx)• Tumor Stage: III vs. IVA• PD-L1 status (TPS \geq 50% vs. TPS<50%) 
This study will be conducted as an open-label study.

Analysis Populations	Efficacy: Intention-to-Treat (ITT) Safety: All Participants as Treated (APaT) PRO: Full Analysis Set (FAS)
Primary Endpoint(s)	Event-free survival (EFS)
Secondary Endpoint(s)	
1. Major pathological response (mPR)2. Overall survival (OS)3. Pathological complete response (pCR)

Statistical Methods for Key Efficacy Analyses	
The primary hypothesis for EFS and key secondary hypothesis for OS will be evaluated by comparing the pembrolizumab arm to the SoC arm using a stratified log-rank test. Estimation of the HR will be done using a stratified Cox regression model. Event rates over time will be estimated within each treatment group using the Kaplan-Meier method.
 
The key secondary hypothesis for mPR will be evaluated by comparing the pembrolizumab arm to the SoC arm with respect to the rate of mPR using the stratified Miettinen and Nurminen method with strata weighting by sample size. The between-treatment difference in percentages, its 95% CI and p-value will be provided.

Statistical Methods for Key Safety Analyses	For analyses in which 95% CIs will be provided for between-treatment differences in the percentage of participants with events, the analyses will be provided using the Miettinen and Nurminen (M&N) method [Miettinen, O. and Nurminen, M. 1985].
Interim Analyses	
Efficacy: Two IAs will be performed. Results will be reviewed by an eDMC. These IAs and the final analysis (FA) are summarized below. Details are provided in Section 10.7.
 
CCI
 
Safety: An interim safety analysis will be performed and reviewed by the eDMC when the first 15 participants in the pembrolizumab arm have completed RT during the post-surgery adjuvant treatment phase. Afterwards, the eDMC will review safety data periodically in the study.

Multiplicity	CCI
Sample Size and Power	
The planned sample size is 714 participants, which will result in approximately 462 participants whose tumors express PD-L1 CPS\geq10 and approximately 680 participants whose tumors express PD-L1 CPS\geq1.
 
CCI

10.2 Responsibility for Analyses/In-House Blinding

The statistical analysis of the data obtained from this study will be the responsibility of the Clinical Biostatistics department of the Sponsor.

The Sponsor will generate the randomized allocation schedule(s) for study treatment assignment for this protocol, and the randomization will be implemented in IVRS.

Although the study is open-label, analyses or summaries generated by randomized treatment assignment and actual treatment received will be limited and documented. Further documentation will be provided in the sSAP. The central pathologists interpreting surgical specimens for assessment of mPR and pCR will be blinded to treatment assignment. In addition, the independent radiologist(s) will perform the central imaging review without knowledge of treatment group assignment.

Blinding issues related to the planned interim analyses are described in Section 10.7.

10.3 Hypotheses/Estimation

Objectives and hypotheses of the study are stated in Section 4.0.

10.4 Analysis Endpoints

Primary and secondary efficacy, safety and PRO endpoints that will be evaluated for within- and/or between-treatment differences are listed below. Exploratory endpoints will be described in the sSAP.

10.4.1 Efficacy Endpoints

10.4.1.1 Primary Efficacy Endpoint

- **Event-free survival (EFS):** the time from randomization to the first of the following events:
 - Radiographic disease progression per RECIST 1.1.
Exception:
 - Participants who undergo a definitive biopsy of the progressed lesion and are found to have no histologic evidence of invasive cancer will not meet criteria for an event.
 - Radiographic disease progression during neoadjuvant phase that precludes surgery will be considered an event.
 - Local or distant progression or recurrence (as assessed with imaging or biopsy as indicated).
 - Death due to any cause.

A secondary malignancy is not considered an EFS event.

See Section 10.6.1 for definition of censoring.

10.4.1.2 Secondary Efficacy Endpoints

- **Major Pathological Response (mPR):** having $\leq 10\%$ invasive squamous cell carcinoma within the resected primary tumor specimen and all sampled regional lymph nodes as assessed by blinded central pathologists.
- **Overall survival (OS):** the time from randomization to death due to any cause.
- **Pathological Complete Response (pCR):** having no residual invasive squamous cell carcinoma within the resected primary tumor specimen and all sampled regional lymph nodes as assessed by blinded central pathologists.

10.4.2 Safety Endpoints

Safety measurements are described in Section 5.4.1.2 Safety Endpoints and Section 9.5.

10.4.3 Patient Reported Outcome (PRO) Endpoints

The following key PRO endpoints will be evaluated as described in Section 5.4.1.3:

- Global health status/QoL and physical functioning scores from the EORTC QLQ-C30

- Symptom sub-scale and single item scores from the EORTC QLQ-H&N35 including the following:
 - problems with swallowing
 - problems with speech
 - pain in the mouth

Additional scales of the EORTC QLQ-C30/QLQ-H&N35 and exploratory PRO endpoints as described in Section 5.4.1.3 will be evaluated. Details will be provided in the sSAP.

10.5 Analysis Populations

10.5.1 Efficacy Analysis Population

The Intention-to-Treat (ITT) population will serve as the primary population for efficacy analyses in this study, which consists of all randomized participants. Participants will be included in the treatment group to which they are randomized for the analysis of efficacy data using the ITT population.

10.5.2 Safety Analysis Population

Safety analyses will be conducted in the All Participants as Treated (APaT) population, which consists of all randomized participants who received study treatment (note that surgery is part of study treatment). Participants will be included in the treatment group corresponding to the study treatment they actually received for the analysis of safety data using the APaT population. This will be the treatment group to which they are randomized except for participants who take incorrect study treatment for the entire treatment period; such participants will be included in the treatment group corresponding to the study treatment actually received.

At least 1 laboratory or vital sign measurement obtained subsequent to at least 1 dose of study treatment is required for inclusion in the analysis of the respective safety parameter. To assess change from baseline, a baseline measurement is also required.

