Treatment Randomization via IVRS		X						Site personnel will access the IVRS after screening and determining if the participant is eligible for randomization. Sites will contact participants and advise of the assigned treatment arm and date of first visit.				
Pembrolizumab Administration			X	X				Treatment 1, Cycle 1 must be given within 3 days of treatment randomization via IVRS. Pembrolizumab to be administered on Day 1 of each cycle after all procedures/assessments have been completed.				
Surgery						X		Performed as part of planned SoC after presurgery imaging. Participants who do not undergo surgery as originally planned, for reasons other than centrally verified radiographic disease progression, may proceed directly to Treatment 2 and receive salvage RT plus cisplatin plus pembrolizumab.				

Study Screening and Treatment 1 Phases (Arm A/Pembrolizumab)												
Study Period	Screening	Treatment randomization	Treatment 1		Presurgery Imaging/ Safety ^c	Surgery ^c	Post-surgery Safety Follow-up	Notes: Participants that discontinue study treatment for reasons other than an event/disease progression will enter post-treatment study follow-up. Participants who discontinue study treatment due to an event/disease progression will enter Safety and Survival Follow-up.				
Visit Number/Title			Pembro neoadjuvant									
Treatment Cycle			1 2									
Week			1 4									
Scheduled Day (s)			1 1									
Scheduling Window (Days, unless noted)			-28 to -1									
Efficacy Procedures			+3 ±3									
CT/MRI head and neck, chest, upper abdomen	X				X*		(X) optional at site discretion	If the participant had received CT/MRI scan prior to providing documented informed consent and within 28 days prior to randomization, the assessment can be accepted. For each participant, the same modality should be used throughout the study for response evaluation. The upper abdominal CT/MRI should cover the liver in its entirety. *Presurgery scans are required within 14 days prior to the date of surgery. Repeat imaging is required if imaging is done >14 days prior to the date of surgery.				
FDG-PET or FDG-PET/CT	X							If the participant had received FDG-PET or FDG-PET/CT scan prior to providing documented informed consent and within 28 days prior to randomization, the assessment can be accepted.				
Tissue Collection for Histopathology (mPR and pCR assessment)						X		Assessment of surgical margins / gross lesions will be performed by the local pathologist.				

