5 STUDY DESIGN

5.1 Overall Design

This is a Phase III, randomized, active-controlled, multisite, open-label study of pembrolizumab as neoadjuvant therapy and pembrolizumab in combination with SoC RT with/without cisplatin as post-surgical adjuvant therapy in treatment naïve participants with newly diagnosed Stage III/IVA, resectable LA HNSCC. The study will be conducted in conformance with Good Clinical Practices (GCP).

714 participants will be enrolled in the study, which will result in approximately 65% (~462) participants whose tumors express PD-L1 CPS \geq 10 and approximately 95% (~680) participants whose tumors express PD-L1 CPS \geq 1, randomized in a 1:1 ratio to:

- Treatment Arm A/pembrolizumab: Pembrolizumab (2 cycles) as neoadjuvant therapy followed by surgical resection followed by adjuvant therapy with pembrolizumab (15 cycles) plus SoC RT \pm cisplatin.
- Treatment Arm B/SoC: No neoadjuvant therapy prior to surgical resection and adjuvant therapy with SoC RT \pm cisplatin (see [Figure 1](#)).

Participants will be stratified by primary tumor site (oropharynx/oral cavity vs. larynx vs. hypopharynx), tumor stage (III vs. IVA), and PD-L1 status (TPS \geq 50% vs. TPS<50%). Stratification factors are described in Section 7.3.1.

A participant's HNSCC status for eligibility at Screening will be based on investigator assessment in accordance with the inclusion/exclusion criteria described in Section 6.1 – Inclusion Criteria and 6.2 – Exclusion Criteria. A formalin-fixed paraffin-embedded (FFPE) tumor tissue sample or slides obtained at a participant's initial diagnosis will be submitted to a designated central laboratory for PD-L1 status determination and for retrospective translational research.

Presurgery neoadjuvant treatment in the pembrolizumab arm (Arm A) should begin within 3 days of randomization or as close as possible to that date on which the participant is allocated or assigned. The timeframe for surgery (after the presurgery visit) is within 6 weeks (\pm 10 days) after randomization. Participants in Arm A are allowed to proceed to surgery outside of this timeframe if the delays are due to an AE. Participants with delays other than for an AE may be considered with Sponsor consultation.

Participants in the SoC control arm (Arm B) will receive no neoadjuvant and will proceed directly to surgery as per local practice.

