5.4.2 Rationale for the Use of Comparator

In this study, the comparator is SoC treatment. In clinical practice, there is no established neoadjuvant therapy for newly diagnosed LA HSNCC, as multiple Phase III studies have

been conducted using various chemotherapy regimens without an established standard. In this study, in the neoadjuvant period, treatment naïve participants will be treated with either pembrolizumab (Arm A) or no therapy before surgery (Arm B). A placebo is not being used in the neoadjuvant treatment period to avoid participant burden and delays in receipt of available recommended surgery/treatment in a high-risk population; participants randomized to no neoadjuvant therapy will go directly to surgery.

In the post-surgery (adjuvant) phase, all participants will be treated with SoC RT ± cisplatin. Treatment with cisplatin will be based on the local pathological assessment of the participant's surgical specimen and their risk for the development of recurrent/metastatic disease post-surgery. In clinical studies, pembrolizumab has demonstrated clinical anticancer activity in patients with recurrent/metastatic HNSCC and in this study its efficacy as an add-on to post-surgery SoC RT ± cisplatin in newly diagnosed HNSCC will be explored.

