9.3 Adverse Events, Serious Adverse Events and Other Reportable Safety Events

The definitions of an adverse event (AE) or serious adverse event (SAE), as well as the method of recording, evaluating, and assessing causality of AE and SAE and the procedures for completing and transmitting AE, SAE and other reportable safety event reports can be found in Appendix 4.

AE, SAEs, and other reportable safety events will be reported by the participant (or, when appropriate, by a caregiver, surrogate, or the participant's legally authorized representative).

The investigator, who is a qualified physician, and any designees are responsible for detecting, assessing, documenting, and reporting events that meet the definition of an AE or SAE as well as other reportable safety events. Investigators need to document if an SAE was associated with a medication error, misuse, or abuse. Investigators remain responsible for following up AE, SAEs and other reportable safety events for outcome according to Section 9.3.3.

Adverse events will not be collected for participants during the pre-screening period (for determination of archival tissue status) as long as that participant has not undergone any protocol-specified procedure or intervention. If the participant requires a blood draw, fresh tumor biopsy etc., the participant is first required to provide consent to the main study and AEs will be captured according to guidelines for standard AE reporting.

9.3.1 Time Period and Frequency for Collecting AE, SAE and Other Reportable Safety Event Information

AEs, SAEs, and other reportable safety events that occur after the participant provides documented informed consent, but before treatment allocation/randomization, must be reported by the investigator if the event causes the participant to be excluded from the trial, or is the result of a protocol-specified intervention, including, but not limited to washout or discontinuation of usual therapy, diet, or a procedure.

- All AEs from the time of treatment allocation/randomization through 30 days following cessation of study treatment must be reported by the investigator.
- All adverse events considered to be post-surgical complications by the investigator from time of protocol-specified surgery through 30 days following surgery, must be reported by the investigator.

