9.10.2.1 Neoadjuvant Treatment (Treatment 1)

Only participants in Treatment Arm A/pembrolizumab will receive neoadjuvant pembrolizumab; participants in Treatment Arm A/pembrolizumab should proceed to surgery directly following the presurgery visit (within 6 weeks [\pm 10 days]) after randomization). Participants in Arm A are allowed to go to surgery outside this timeframe if delays are due to an AE. Participants with delays other than for an AE may be considered with sponsor consultation. Participants in the Treatment Arm B/SoC will proceed directly to surgery following within 4 weeks after randomization.

Visit timing requirements during the treatment period for Arm A are as follows:

- Assessments/procedures should be performed on Day 1 for each cycle.
- Pembrolizumab treatment cycles are 3 weeks (21 days).
- The window for each visit is \pm 3 days, unless otherwise noted. Cycle 1 treatment should begin within 3 days of randomization or as close as possible to that date on which the participant is allocated or assigned.

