9.10.2.2 Definitive Surgery

All participants will have presurgical assessments performed at Week 0-4 (\pm 10 days) for the SoC arm (Arm B) or Week 6 (\pm 10 days) for the pembrolizumab arm (Arm A), to allow assessment of disease status, PROs and safety monitoring. The window for this visit allows participants to proceed to surgery up to 10 days earlier or later if deemed necessary by the investigator.

Definitive surgery will be performed as per local SoC (Arm B/SoC) and following completion of neoadjuvant treatment (Arm A/pembrolizumab). Note: Participants in the pembrolizumab arm (Arm A) may proceed to surgery after 1 dose of pembrolizumab, if deemed appropriate, if the investigator has documented clinical evidence of tumor progression, preferably supported by radiographic evidence.

Participants who do not undergo surgery as originally planned may proceed directly to Treatment 2 and receive salvage RT plus cisplatin \pm pembrolizumab, depending on treatment assignment at the discretion of the investigator in consultation with the Sponsor.

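### The safety population admits Arm A at the first infusion but Arm B only at surgery or RT, so Arm B participants who reach neither drop out of every planned safety table

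*Combined protocol and SAP*

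**What the plan says.** Section 10.5.2 restricts safety analyses to a population "which consists of all randomized participants who received study treatment (note that surgery is part of study treatment". Only efficacy uses all randomized participants (Section 10.5.1).

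The two arms reach first study treatment at different times:

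- **Arm A.** Section 5.1: "Presurgery neoadjuvant treatment in the pembrolizumab arm (Arm A) should begin within 3 days of randomization", or as near to that date as possible. The schedule in Section 2.1 is firmer: "Treatment 1, Cycle 1 must be given within 3 days of treatment randomization via IVRS". Surgery comes later: "The timeframe for surgery (after the presurgery visit) is within 6 weeks (\pm 10 days) after randomization".
- **Arm B.** There is no neoadjuvant treatment and no placebo (Section 5.4.2): "participants randomized to no neoadjuvant therapy will go directly to surgery". Section 9.10.2.1 gives the timing: "Participants in the Treatment Arm B/SoC will proceed directly to surgery following within 4 weeks after randomization".
- **No surgery.** Section 9.10.2.2: "Participants who do not undergo surgery as originally planned may proceed directly to Treatment 2 and receive salvage RT plus cisplatin", with or without pembrolizumab according to assigned arm.

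Event collection is the same in both arms and starts before treatment. Section 9.3.1: "All AEs from the time of treatment allocation/randomization through 30 days following cessation of study treatment must be reported by the investigator". SAEs are also collected from randomization.

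Sections 10.5.2 and 10.6.2 and Table 15 specify neither a safety summary in all randomized participants nor a separate presurgical summary.

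**The concern.** Entry to APaT in Arm B depends on something that happens after randomization: staying alive, fit and willing long enough to reach an operation or radiotherapy. Entry in Arm A depends on this for only about 3 days. The same early course is therefore handled differently by arm, and the comparison of early harm is not a randomized one for the participants affected.

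This matters most before surgery. Neoadjuvant pembrolizumab is then the only planned treatment difference, and safety of the neoadjuvant phase is part of Objective 6. Deaths among the excluded Arm B participants still count in EFS and OS. Their SAEs and Grade 3-5 events appear in no analysis specified in these documents. The trial is open-label, so withdrawal after learning of a control assignment is another route by which Arm B participants could be lost.

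**Working it through.** The documents give no figure that depends on this definition, and the sample size section is redacted, so there is nothing to reproduce. The check is a comparison of rules followed by an illustration.

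**Step 1. Same course, two arms.** Take a participant who has a serious event on day 10 and receives no further study treatment.

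| | Arm A | Arm B |
|---|---|---|
| Event collected (9.3.1)? | Yes | Yes |
| Study treatment received by day 10? | One infusion, if dosed on schedule | None, if not yet operated on |
| In APaT (10.5.2)? | Yes | No |

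If the Arm B participant is later operated on or irradiated, he or she enters APaT and the day-10 event counts, because collection began at randomization. Only Arm B participants who receive neither are lost.

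**Step 2. Exposure to exclusion.** There are 714/2 = 357 participants per arm. Let q be the 28-day risk of a treatment-preventing event, equal in both arms, with constant hazard (assumed). Expected exclusions are 357 × [1 − (1 − q)^(3/28)] in Arm A and up to 357 × q in Arm B.

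| q | Arm A excluded | Arm B excluded |
|---|---|---|
| 1% | 0.4 | 3.6 |
| 2% | 0.8 | 7.1 |
| 3% | 1.2 | 10.7 |

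The Arm B figures take surgery at day 28 and no salvage RT, so they are upper values. Arm A has a gap of its own, but a small one.

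**Step 3. Effect on the any-SAE row.** Let k be the number per arm with a treatment-preventing SAE: 4, 7 or 11, about 1%, 2% and 3% of 357. Let the SAE risk in everyone else be s = 30% (assumed). Ignoring Arm A's small gap, Arm A shows [k + s(357 − k)]/357 and Arm B shows s. The difference is (k/357)(1 − s).

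| k | Arm A | Arm B | Difference (points) | Miettinen-Nurminen 95% CI |
|---|---|---|---|---|
| 4 | 110/357 = 30.8% | 106/353 = 30.0% | 0.8 | −6.0 to 7.6 |
| 7 | 112/357 = 31.4% | 105/350 = 30.0% | 1.4 | −5.4 to 8.2 |
| 11 | 115/357 = 32.2% | 104/346 = 30.1% | 2.2 | −4.7 to 9.0 |

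The true difference is zero in every row.

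**Step 4. Early deaths.** If the k events are deaths before any Arm B treatment, the early period shows 4/357 = 1.1%, 7/357 = 2.0% or 11/357 = 3.1% in Arm A against 0% in Arm B, again with equal true risk.

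**Step 5. One rule for both arms.** Counting all randomized participants from randomization gives 357 in each denominator and the same expected rate. The artefact is then zero.

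**The case against.** The strongest reply is that few people are affected and no formal conclusion is at risk. Unoperated Arm B participants may receive salvage RT plus cisplatin and so enter APaT with their earlier events. Deaths are in the ITT analyses of EFS and OS. Section 10.6.4 displays the number randomized and the main reason for discontinuation. SAEs go to the sponsor within 24 hours, and Table 17 puts AEs and surgical delays before the DMC. The sSAP and DMC charter are not in these documents and may add a listing. The bias also makes pembrolizumab look worse, so it hides no harm.

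Most of this stands, and it limits the size of the problem. It does not remove the asymmetry. DMC review and expedited reporting are not commitments to a table by arm, and the contents of unseen documents cannot be assumed.

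A reader might go further and infer that a handful of such events would produce a false treatment difference whose confidence interval excludes zero. Comparing 4/357 with 0/353 gives 1.1% (0.04% to 2.9%). The documents do not support that reading:

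- Table 15 plans descriptive statistics only for death, any SAE and any Grade 3-5 AE. Treatment-comparison intervals are limited to specific AEs at 10% or more, and specific Grade 3-5 AEs or SAEs at 5% or more. Section 10.6.2 calls those intervals descriptive.
- Setting Arm B to zero assumes that no treated participant has the event at any time in the study. Step 3 shows what happens with a realistic background. Even a death row with only four later deaths per arm gives 1.1 points (−0.9 to 3.4) for k = 4 and 1.9 (−0.2 to 4.4) for k = 7. At k = 11 the interval would exclude zero (0.7 to 5.8), but that needs the top of an assumed range and an interval that the plan does not produce.

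It would also be wrong to say that no Arm A participant is lost. Events between randomization and the first infusion that prevent dosing are excluded there too.

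**Conclusion.** The point holds in a limited form. As written, APaT entry is conditional on a post-randomization outcome for up to about 4 weeks in Arm B and about 3 days in Arm A, and no planned safety table covers those left out. The direction is against pembrolizumab.

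The size is unknown, because the documents give no rate for presurgical events that prevent all treatment. With 1% to 3% per arm and a 30% background SAE risk, both assumed, the any-SAE row moves by about 0.8 to 2.2 points, which is modest beside its sampling error. The distortion is clearest for early deaths and other presurgical events, where equal risks of 1% to 3% would appear as 1% to 3% against 0%. No planned test or interval on the overall rows is falsified. This is a worthwhile, inexpensive improvement to safety reporting and does not threaten the trial's main conclusions.

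**What to change.** Keep APaT as the main safety population and add to Sections 10.5.2 and 10.6.2:

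1. By arm, the number of randomized participants outside APaT, the reason, and their AEs, SAEs and deaths.
2. A supplementary summary of any AE, Grade 3-5 AE, SAE and death in all randomized participants by assigned arm, counted from randomization over the whole course.
3. A presurgical summary in all randomized participants, from randomization to surgery, or to first RT if there is no surgery. Express it per person-time, because the planned presurgical interval differs by arm. Report the number without surgery, by reason, over each arm's full presurgical period.

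A common cut at day 28 should not be used for the presurgical summary. Arm B surgery is due by day 28, while Arm A surgery is due at 42 ± 10 days, that is days 32 to 52. Such a window would take in most Arm B operations and their early complications but almost no Arm A operations, and would favour pembrolizumab.

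The cost is SAP wording and a few extra tables from data already collected under Section 9.3.1, with no change to trial conduct. The small downside is that the supplementary summaries include a few Arm A participants who never received pembrolizumab.
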